Intervention - Phase 4: Patients in arm 2 will begin receiving text messages per a pre-determined protocol starting 7 days prior to the date of scheduled colonoscopy (the text messaging protocol is attached to this application). Of note, if a patient in arm 2 cancels or reschedules their colonoscopy after randomization, they will not receive any additional protocol text messages as part of this trial. Patients in arm 1 and arm 2 will both receive usual care, which includes (1) bowel preparation instructions that are delivered via mail or through a secure online messaging portal, (2) a phone call from the endoscopy

staff in the week prior to colonoscopy, and (3) the option to call the endoscopy staff during business hours to have any questions answered on demand.

Outcomes data collection - Phase 5: After a patient's scheduled colonoscopy date has passed, the research coordinator will review the medical record to gather additional data from the endoscopy procedure. This will include the indication for the procedure, quality of bowel preparation (rescue, poor, fair, adequate, good, excellent; Boston Bowel Prep Score will also be collected if recorded), and completeness (cecum reached). Procedure status will also be recorded (canceled, no-show, rescheduled, completed). If the procedure was canceled, the cancellation lead time (in days) prior to scheduled colonoscopy will be recorded.

Statistical Analysis and Manuscript Preparation - Phase 6: The statistical analysis (detailed below) will commence after completion of outcomes ascertainment for the entire cohort.

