##### **Potential Study Benefits**

The benefits of this study for participants include a platform that may improve the bowel preparation experience prior to colonoscopy and increase the likelihood that a colonoscopy will not be hindered by inadequate preparation or a missed/canceled appointment. This will occur through a set of curated text messages with timely reminders as well as information with online links and a phone number to improve accessibility for questions to be answered on a timely basis. It is also possible that the benefits for some participants will be minimal. However, as mentioned, we believe the risks are also minimal. The control group is unlikely to directly benefit, as this group will continue to receive usual care. The potential public health impact of a successful intervention to improve colonoscopy show rates and bowel preparation quality is significant and could increase the chances of identifying colorectal cancer at an early stage and reduce the number of repeat colonoscopies and related costs due to inadequate bowel preparation. Information learned from this study may benefit society through a better understanding of how to

effectively increase the rate of adequate colonoscopies which could increase the rate of colorectal cancer screening and reduce the rate of mortality.

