## Final Statistical Analysis Plan

**\*\*New changes from initial protocol notated in bold, parts removed from initial protocol notated in strikethrough**

The target enrollment sample size is 750 patients—375 in arm 1 (usual care) and 375 in arm 2 (usual care plus texting intervention). This number is based in part on sample size calculations using data from a previous pilot, which suggests that a total sample size of 750 patients will have greater than 80% power to detect a 10% difference in the primary outcome. We also chose a larger sample size to account for the fact that some patients enrolled in arm 2 may opt out of receiving text messages, which would likely decrease the effect size between arms.

Descriptive analysis will include comparison of baseline demographics and major medical comorbidities between study arms. Continuous and categorical data will be compared using the Wilcoxon Rank-sum and Chi-squared tests, respectively. An alpha threshold of 0.05 will be used for statistical significance, with two-tailed testing performed in all instances. For the primary analysis, we will perform a Chi-squared test of independence to compare the proportion of colonoscopies with good/excellent bowel preparation between groups. In the secondary analysis, Chi-squared tests of independence will be performed to compare colonoscopy status (show, no-show, reschedule, cancellation) as well as bowel preparation quality (excellent, good, adequate, fair, poor) between groups. Among canceled colonoscopies, median lead time of cancellation will be compared between groups using the Wilcoxon Rank-sum test. Finally, for both primary and secondary analyses, we will consider multivariable regression modeling to adjust for imbalances in possible confounders, if present despite randomization.

Deleted: 40  
Deleted: 200  
Deleted: 200  
Deleted: 20  
Deleted: 5  
Deleted: .

Deleted: Finally, a

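### Cancellation lead time is tested only among patients who cancel, a group the texts aim to change, so the p-value is not a randomised comparison of notice and the result should be descriptive.

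*Combined protocol and SAP*

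**What the plan says.** The Final Protocol, under Secondary outcome variable(s), lists the cancellation rate, the no-show rate and the number of days' notice of cancellation as separate secondary outcomes. The only planned analysis of days of notice is in the Final Statistical Analysis Plan and is repeated in the Final Protocol's Analysis Plan: "Among canceled colonoscopies, median lead time of cancellation will be compared between groups using the Wilcoxon Rank-sum test". Like every other test in the plan, it is two-sided at 0.05. Nothing labels it descriptive or exploratory.

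Four other statements bear on it:

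- The same paragraph tests status as an outcome: "Chi-squared tests of independence will be performed to compare colonoscopy status (show, no-show, reschedule, cancellation".
- Potential Study Benefits says the programme may "increase the likelihood that a colonoscopy will not be hindered by inadequate preparation or a missed/canceled appointment".
- Procedures, Phase 4: "Patients in arm 2 will begin receiving text messages per a pre-determined protocol starting 7 days prior to the date of scheduled colonoscopy". Key exclusion criteria require at least 14 days between enrolment and the procedure.
- Procedures, Phase 5: "If the procedure was canceled, the cancellation lead time (in days) prior to scheduled colonoscopy will be recorded". No value is defined for patients who attend or do not show.

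**The concern.** Randomisation makes the two arms comparable as randomised. It does not make the cancellers in one arm comparable with the cancellers in the other if the intervention affects who cancels, and affecting that is one of its aims. The bias has no fixed direction:

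- A patient who would not have shown, but who after the texts cancels three days ahead, gives the clinic more notice than before. That patient enters arm 2's canceller group at the short end and pulls its median down.
- A patient who would have cancelled late, but who now attends, leaves the short end of arm 2's group. The median rises although nobody gave earlier notice.

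The adjustment clause does not help: "we will consider multivariable regression modeling to adjust for imbalances in possible confounders, if present despite randomization". It concerns chance imbalance at baseline, not selection that the treatment itself causes. The intention-to-treat statements in Accrual and Procedures deal only with patients who opt out of the texts.

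At stake is a listed secondary outcome. Its only test can be significant in either direction, including against the texts when notice improved, or stay flat when no-shows are halved.

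**Working it through.** **Inputs from the documents.** 375 per arm and two-sided alpha 0.05 (Final Statistical Analysis Plan); cancellation means at least one day ahead (Secondary outcome variable(s)); texts start 7 days ahead (Procedures); baseline show rate about 50% (Background).

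**The plan's own figure.** It gives none for lead time. For the primary outcome it claims "greater than 80% power to detect a 10% difference in the primary outcome". With

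z = [d√n − 1.96·√(2p̄(1−p̄))] / √(p₁(1−p₁) + p₂(1−p₂)),

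50% against 60% gives z = (0.1·19.36 − 1.96·0.7036)/0.70 = 0.80, a power of 78.7%. Over control rates of 30% to 80%, power runs from 78.3% to 97.1%, so the claim is roughly reproduced. The present point does not depend on it.

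**Assumed, because the documents are silent.** 25% cancel and 20% do not show; lead time is uniform over 1-28, 1-21 or 1-14 days. Expected numbers per arm are 0.25·375 = 93.75 cancellers and 0.20·375 = 75 no-shows.

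**Step 1: half of no-shows become cancellations at 1-6 days.** Arm 2 has 93.75 + 37.5 = 131.25 cancellers, so the median sits at the 65.6th. Of these, 37.5 are converted patients at 6 days or less, leaving 28.1 of the 93.75 original cancellers, a fraction of 0.30. On 1-28 days that point is 0.5 + 0.30·28 = 8.9 days, against 14.5 in arm 1: a shift of −5.6 days. The simulated shifts are −5.6, −4.1 and −2.0 days for the three ranges.

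**Step 2: half of cancellations at 6 days or less become attended visits.** On 1-28 days, 93.75·(6/28)·0.5 = 10.0 cancellers leave and 83.7 remain, so the median is at the 41.9th. Of these, 10.0 are late, and the other 31.8 at 93.75/28 = 3.35 per day take 9.5 days past day 6.5. The median is 16.0 days, against 14.5: a shift of +1.5. The show rate rises by 0.25·(6/28, 6/21 or 6/14)·0.5 = 2.7, 3.6 or 5.4 points, well short of the 10-point primary difference.

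**Step 3: how often the planned test rejects.** Simulation, 4,000 trials per cell, Monte Carlo standard error below 1 point. 'Worse' means significantly shorter lead time in arm 2; 'late' means 6 days or less.

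| What the texts do | Test says of arm 2 | 1-28 d | 1-21 d | 1-14 d |
|---|---|---|---|---|
| Nothing | either way | ~5% | ~5% | ~5% |
| 1/2 of no-shows cancel at 1-6 d | worse | 83% | 76% | 57% |
| 1/4 of no-shows cancel at 1-6 d | worse | 35% | 31% | 22% |
| 1/10 of no-shows cancel at 1-6 d | worse | 11% | 9% | 8% |
| 1/2 of no-shows cancel, any lead time | either way | ~5% | ~5% | ~5% |
| 1/2 of late cancellations attend | better | 19% | 26% | 41% |
| 1/4 of late cancellations attend | better | 7% | 9% | 12% |
| 1/4 of no-shows cancel at 1-6 d and 1/2 of late cancellations attend | worse | 12% | 6% | 2% |
| 1/2 of no-shows cancel at 1-6 d and 1/2 of late cancellations attend | worse | 62% | 46% | 20% |

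**Step 4: the same trials, no-shows compared in all randomised.** With half converted, 20% against 10% gives z = (0.1·19.36 − 1.96·0.505)/0.50 = 1.89, a power of 97%. The simulation also gives 97%. So in the fifth row of the table the lead-time test sees nothing while the no-show comparison almost always detects the change. With a quarter converted the no-show comparison detects it in 42-45%, and with a tenth in 10-11%.

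**Step 5: other splits.** With both shifts and a quarter of no-shows converted, the test says better in 8/14/32% at 40% cancel and 10% no-show, but worse in 44/33/12% at 20% and 30%. Setting non-attendance at 50%, with splits from 40/10 to 20/30, arm 2 is called worse in 17-98% (half of no-shows converted to 1-6 days), 7-68% (quarter) or 4-21% (tenth), and better in 16-60% if half of late cancellations attend.

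**Step 6: a different lead-time model.** With 20% cancelling, half of them at 1-7 days and the rest at 8-21, and 15% no-shows of whom a quarter or half cancel 1-2 days ahead, the average median falls from 7.9 to 6.2 days or from 7.8 to 4.9. The test rejects in 32% or 76%.

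Same-day cancellations and reschedules were not simulated.

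**The case against.** The restriction is stated openly, lead time exists only for cancellers, and the status test in the same paragraph shows the reader any change in who cancels. The test keeps its level when the texts change nothing, so a rejection is valid evidence that they changed who cancels or when. The largest percentages need converted no-shows to cancel in the last 6 days, yet arm 2 also receives two messages at enrolment, at least 14 days ahead. If half of a converted quarter cancelled at any lead time, 'worse' would drop from 37/28/23% to 10/9/8%. Lower base rates also weaken the effect: at 15% cancelling and 10% not showing, a quarter converted gives 18/14/12%. Finally, the proposed replacement does not measure days of notice, and a sentence of caution could serve while keeping the test.

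Much of this stands as a limit on size. The figures show what can happen, not what is likely, and the no-effect level is not in dispute. It does not remove the point. Seeing the status distribution does not let a reader separate who cancelled from how early, and a p-value for a listed outcome will be read as an effect on notice. Attenuation is not elimination: at 15/10 with half converted, 'worse' is still 50/44/30%. A caution would help, but it leaves a test whose direction cannot be interpreted if the texts work as intended.

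**Conclusion.** The concern holds. The lead-time test conditions on a post-randomisation status that the texts aim to change, and nothing in the plan corrects for that. It is a valid test only of the strict hypothesis that the texts change neither who cancels nor when; it is not a randomised comparison of notice. Size and direction rest on assumed rates: in the scenarios examined, misleading significance ranges from close to the 5% level when few patients shift, or when opposite shifts offset each other, to 98% at the extreme. One secondary outcome is affected and the primary outcome is not, so this is a change that should be made rather than a threat to the trial. Confidence is high on the principle and much lower on the magnitude.

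**What to change.** In the Final Statistical Analysis Plan and the Final Protocol's Analysis Plan:

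1. Report median lead time among cancellers by arm as a description, without a between-arm test, beside the status distribution in all randomised patients.
2. Base any conclusion on notice on the proportion of all randomised appointments lost without advance notice (no-show or same-day cancellation), with a risk difference and 95% confidence interval. State that this largely overlaps the listed no-show rate and does not measure days of notice.

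Two definitions need a line each, as clarification only. Phase 5 keeps the categories apart ("Procedure status will also be recorded (canceled, no-show, rescheduled, completed"), but the wording for a cancellation in Secondary outcome variable(s) also fits a reschedule, and a same-day cancellation has no stated category. Keep the existing reschedule definition, keep as cancelled a patient who cancels at least a day ahead and rebooks on a later day, code same-day cancellations with no-shows, and say whether reschedules enter the lead-time summary.

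The cost is wording and one coding rule at chart review, with no extra patients or data source. If reschedules are included, their lead time must also be recorded, since Phase 5 now asks for it only when a procedure was cancelled. What is lost is a formal test of days of notice.

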### Study Design

#### Design

We will perform a pragmatic randomized controlled trial evaluating the impact of the text message-based intervention (arm 2) as compared to usual care alone (arm 1). Patient enrollment will proceed through two pathways (early phase and late phase). In the early phase, 250 patients will be enrolled through, or through phone calls from a clinical research coordinator, using a script pre-approved by the University of Pennsylvania Institutional Review Board. After enrollment, patients will be randomized 1:1 to the arms listed above through the Way to Health platform. Although patients in arm 2 may be enrolled more than one week in advance of their colonoscopy, they will only receive intervention text messages in the 7 days prior to the scheduled colonoscopy, in addition to two text messages at the time of enrollment explaining the texting program. Usual care consists of a phone call from the PPMC endoscopy staff in the week prior to colonoscopy, if the patient is able to be reached. Patients are also given the endoscopy phone number, and may call to speak to staff if they have specific questions about their colonoscopy or need to reschedule. In the late phase, an additional 500 patients will be automatically enrolled in the Way to Health system using verified cell phone numbers from the electronic medical record system, where they will be randomized in a 1:1 ratio to the study arms in variable blocks of 8 and 4. Patients in arm 2 will receive two enrollment text messages explaining the texting program and providing the opportunity to opt out (by replying with the text STOP). A detailed outline of the study design can be found in the procedures sections.

**Deleted:** be performed with assistance from the call center at the Pennsylvania Presbyterian Medical Center (PPMC), and/

**Deleted:** s or months

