**Deleted:** Patients who have a physician order for a colonoscopy will call the PPMC call center in order to schedule their procedure. At this time, the call center staff will screen the patient for eligibility (age criteria and text messaging ability) and will explain the details of the study following a pre-determined script. Patients who agree to participate in the study will have their cell phone number recorded. A list of these patients will be forwarded to the clinical research coordinator on a weekly regular basis, who will confirm patient eligibility and then manually enter patients into the WTH platform for randomization. Alternatively,

**Deleted:** for

Randomization - Phase 2: In the early phase, using a random number generator in the WTH platform, patients will be 1:1 randomized to arm 1 or arm 2. Beginning in the late phase of enrollment, patients will be randomized to arm 1 or arm 2 in a 1:1 ratio in variable blocks of 8 and 4 using the WTH platform, until the target sample size of 375 patients per arm is reached.

**Deleted:** between 500 and

**Deleted:** 6

**Deleted:** 40

**Deleted:** , until the target

**Deleted:** sample size of 200 patients per arm is reached. Randomization will be performed and recorded in WTH.

Chart review - Phase 3: after randomization and in tandem with phase 4 (below), the research coordinator will perform a chart review to obtain patient demographic and comorbidity data (hypertension, hyperlipidemia, diabetes, inflammatory bowel disease, obesity, active opiate prescription). We will also collect data on the number of patients opting out in the late phase of enrollment, as well as data on nursing phone calls which are performed as a component of usual care (not called, called but could not reach patient, called and spoke with patient). All data will be inputted into and stored in a secured RedCap database. Only key study staff will have access to the RedCap database, which is stored on a secure firewall-protected server.

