#### **Analysis Plan**

Descriptive analysis will include comparison of baseline demographics and major medical comorbidities between study arms. Continuous and categorical data will be compared using the Wilcoxon Rank-sum and Chi-squared tests, respectively. An alpha threshold of 0.05 will be used for statistical significance, with two-tailed testing performed in all instances. For the primary analysis, we will perform a Chi-squared test of independence to compare the proportion of colonoscopies with good/excellent bowel preparation between groups. In the secondary analysis, Chi-squared tests of independence will be performed to compare colonoscopy status (show, no-show, reschedule, cancellation) as well as bowel preparation quality (excellent, good, adequate, fair, poor) between groups. Among canceled colonoscopies, median lead time of cancellation will be compared between groups using the Wilcoxon Rank-sum test. Finally, for both primary and secondary analyses, we will consider multivariable regression modeling to adjust for imbalances in possible confounders, if present despite randomization.

**Deleted:** Finally, a

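### Imbalance-triggered regression is allowed for the primary analysis without being labelled supportive, and the primary test ignores the two separately randomised phases: minor, and nearly free to correct

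*Combined protocol and SAP*

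**What the plan says.** **Primary test.** The Analysis Plan of the Final Protocol and the Final Statistical Analysis Plan agree: "For the primary analysis, we will perform a Chi-squared test of independence". The significance rule is "An alpha threshold of 0.05 will be used for statistical significance, with two-tailed testing performed in all instances". Neither text includes a stratum or covariate for phase.

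**Regression.** Both texts close by saying, for primary and secondary analyses together, that "we will consider multivariable regression modeling to adjust for imbalances in possible confounders, if present despite randomization". The initial SAP has no such sentence, and the Summary of Statistical Analysis Plan Modifications lists it as an added possibility. Neither text defines imbalance, names adjusters or a model, or says which result stands if the two differ. Chart review (Procedures, Phase 3) will "obtain patient demographic and comorbidity data (hypertension, hyperlipidemia, diabetes, inflammatory bowel disease, obesity, active opiate prescription" but does not make these adjusters. Baseline variables are compared between arms by Wilcoxon and chi-squared tests, with no stated link to the decision to adjust.

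**Phases.** The first 250 patients are enrolled by coordinator telephone call. Then: "In the late phase, an additional 500 patients will be automatically enrolled in the Way to Health system". The Randomization paragraph of Procedures says: "In the early phase, using a random number generator in the WTH platform, patients will be 1:1 randomized to arm 1 or arm 2". Late-phase patients are "randomized to arm 1 or arm 2 in a 1:1 ratio in variable blocks of 8 and 4", and this continues "until the target sample size of 375 patients per arm is reached".

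**The concern.** Two separate matters arise.

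1. Whether an adjusted primary result exists, and which one, would be settled after the baseline table is seen. No sentence makes it subordinate to the chi-squared test. If the two disagreed, the plan would not state in words which is the trial's answer.

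2. The phases differ in enrolment route, calendar time and allocation method, and the protocol's own case for a consent waiver (Waiver Essential to Research) says that patients who answer the telephone may be more motivated. Success rates may therefore differ by phase. Analysis would normally follow the separately randomised strata. Ignoring them can cost a little power and, depending on how the 375-per-arm target is met, move type I error slightly.

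**Working it through.** **Inputs from the documents.** 750 patients, 375 per arm, two-sided alpha 0.05, a 10-point difference, early phase 250, late phase 500, six listed comorbidities.

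**Assumed, because the documents give no figure.** Control rate of the primary outcome (the protocol gives only a baseline show rate of about 50%, a different quantity), the gap g in success rate between phases, and covariate prevalence and strength. All calculations count all 750 randomised patients.

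**The plan's own figure.** Power = Φ{[δ√n − 1.96√(2p̄(1−p̄))] / √(p₁(1−p₁)+p₂(1−p₂))}. With n=375, p₁=0.45, p₂=0.55: (1.9365 − 1.3859)/0.7036 = 0.783, so 78.3%. This is the lowest value over control rates of 20-80%; the highest is 97.1% at 80%. The stated figure of more than 80% is reproduced to within 2 points.

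**Phase, analytically (g = 0.20, standard error 3.65 points).**
- Share of outcome variance between phases: (1/3)(2/3)g²/0.25 = 3.6% (0.9% at g = 0.10).
- The early count in one arm is Binomial(250, 0.5): SD √62.5 = 7.9, 95% range about 110-140.
- Reading A, late phase 250 per arm. A 1-SD early imbalance gives early shares of 132.9/382.9 = 0.347 and 117.1/367.1 = 0.319, a difference of 0.028, which shifts the result by 0.56 points. Variance relative to what the pooled test assumes: 1 − 0.036 + (0.56/3.65)² = 0.99.
- Reading B, late phase offsets early imbalance to 375 per arm. The share difference is 15.8/375 = 0.042, a shift of 0.84 points. Relative variance: 1 − 0.036 + (0.84/3.65)² = 1.02.

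The pooled test is thus about right or slightly conservative under A, and slightly liberal under B. The shift averages zero over randomisations.

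**Phase, by simulation** (400,000 trials per setting, control rate 45%, gaps in either direction, no continuity correction):

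| Assumed gap (points) | A: pooled type I error | B: pooled type I error |
|---|---|---|
| 0-10 | about 5.0% | about 5.2% |
| 20 | 4.9% | 5.4% |
| 30 | 4.7-4.8% | 5.6-5.7% |

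The stratified test stays at 4.9-5.1% throughout. Under B the pooled rate is already a little above 5% with no gap, because the test is discrete with exactly equal arms, so not all of the excess comes from phase. Stratifying changes power for a 10-point effect by −0.2 to about 0 (A) or −0.6 to −0.1 (B) at gaps of 0-10, and by about +0.8 to +0.9 at 20.

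**Conditional adjustment under a fixed rule** (20,000 trials per setting, control rate 45%, six independent binary covariates at 30% prevalence, R² 2, 5 or 10%; covariates with baseline p<0.05 enter a linear risk-difference model):
- Chance of a trigger: 1 − 0.95⁶ = 26.5%; with age and sex added, 1 − 0.95⁸ = 33.7%.
- When triggered, the risk difference moves by a median of 0.5, 0.8 or 1.1 points (95th percentile 1.1, 1.5, 2.0) for the three R² values.
- At a 10-point effect the two results disagree on significance in 4.5-8.9% of triggered trials, or 1.2-2.3% of all trials.
- Taking the better of the two results adds about 0.1-0.4 points to type I error. With nine covariates (odds ratios 1.2-2.0) the addition is 0.3-0.6 points, for example 5.46 − 5.15 and 5.56 − 4.99.

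**Conditional adjustment with free choice.** Taking the best result across thresholds 0.05, 0.10, 0.20 and all covariates gives type I error of 5.6-6.5% with six covariates and 6.2-7.5% with nine. Taking the best covariate subset gives 6.5-8.9% and 7.2-12.5%. A model with phase and all nine covariates fixed in advance stays at 4.8-5.4%.

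**The case against.** The strongest reply has four parts.

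- **Chi-squared is already the primary test.** Regression is only something to be considered. This stands: a reader might infer that the trial has no defined primary result, and the texts do not support that. What is missing is a sentence making the adjusted result supportive, and a fixed model.
- **The trigger is partly given.** The SAP names the kinds of variable compared at baseline, the tests and alpha 0.05 in all instances. This stands in part: p<0.05 is a fair guess and is used above, but no sentence ties it to adjustment.
- **The phase point is close to preference.** The pooled test is valid under Reading A. Reading B would require closing one arm near the end, which the blocked 1:1 description and the fixed 500 late patients do not suggest. This largely stands. A reader might infer that the pooled test is biased or invalid; it is not. The case for stratifying is that it follows the randomisation, holds type I error near 5% on either reading and costs almost nothing.
- **The large type I error figures need deliberate searching.** They do, and nothing in the documents suggests that this is intended. They bound what the wording permits; they do not predict conduct.

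Nor is this an intention-to-treat problem: Accrual and Procedures keep late-phase opt-outs in the intervention arm.

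**Conclusion.** The point holds as a minor one, with two parts of different size.

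- **Regression.** The sentence permits a data-prompted adjusted primary result without ranking it below the chi-squared test. The effect is small under a fixed p<0.05 rule. It is not small in general: free choice of threshold could bring type I error to about 6-7.5%, and free choice of covariate subset higher still. These are worst cases that rest on assumed covariate number, prevalence and strength.
- **Phase.** Ignoring phase introduces no bias and does no harm to validity if the late phase is 250 per arm. Type I error rises slightly only if the 375-per-arm target is met by offsetting early imbalance. The size depends on phase gaps that the documents do not give.

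Which patients form the denominator of the primary outcome is a separate question and is not judged here.

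**What to change.** Change the Analysis Plan of the Final Protocol and the Final SAP together.

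1. Analyse the primary outcome with a Cochran-Mantel-Haenszel test stratified by enrolment phase, without continuity correction, patients in their assigned arms. Report the Mantel-Haenszel risk difference with 95% CI, and state that this result governs.
2. Replace the conditional regression sentence with one supportive model fixed in advance: phase, age, sex and the six chart-review comorbidities, or a subset justified before the data are seen. Report it as a standardised risk difference with 95% CI, whatever the baseline comparison shows.
3. Show risk differences by phase descriptively only, since phase is confounded with calendar time, enrolment route and allocation method.

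**Cost.** SAP wording and a few lines of code; no extra patients and no new data. Phase is known for everyone and the comorbidities are already collected; sex is assumed to be among the demographic data. The price is at most about 0.6 points of nominal power if phase is not prognostic, against a gain of about 0.8-0.9 points at an assumed 20-point gap.
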